Title: The implementation of a community-health focused intervention using combined aerobic and resistance training protocols in a group setting.

NCT number (not available)

February, 23, 2023

Title: The Implementation Of A Community Health-focused Intervention Using Combined Aerobic and Resistance Training Protocols In A Group Setting

1. Research Design/Methods

- a. The purpose of this project is to provide an intervention focused on a combination of aerobic and resistance training exercise for adults residing in Somerset County, Maryland. Through a pre-determined, structured exercise program, participants will engage in physical activity sessions for 12 weeks. The program will be offered from January 9-March 31, 2022. This approach is appropriate as Somerset County has the highest physical inactivity level and poorest physical health amongst surrounding counties (CHNA, 2019). Currently, Somerset County residents only have access to fitness classes, offered twice a week, which take place in a classroom at Somerset Technical High School. The class is offered through Somerset County Recreation, Parks, and Tourism and interested participants pay a fee to join. However, this project offers participants pre and post assessments and monitored aerobic and resistance training sessions with a primary outcome of improving body weight, body composition and/or measures of fitness.

2. Subject Selection

- a. The subjects are adults, 18 years or older, residing in Somerset County. There is not an upper age limit to participate in the program. Funding for this project requires activities that address the poor health outcomes of adults in Somerset County, Maryland. Somerset County Health Department will assist in advertising for the project as the intervention is open to adults, 18 years of age or older, in Somerset County.
- b. Flyers will be posted around Somerset County. Somerset County Parks & Recreation will be contacted and sent a flyer. The flyer is attached.
- c. Subjects will be recruited from Somerset County, Maryland. This is a requirement for the funding that was received for the project. The PI will ask surrounding businesses and organizations permission to post the project flyer.
- d. Somerset County Health Department will assist in advertising for the project. Subjects are not being selected based on any specific characteristic(s). Any interested adult in Somerset County can participate. The project is limited to 15 individuals and therefore participation is on a first come-first serve basis.
- e. The project will be advertised through Somerset County Health Department and the surrounding businesses and organizations. All interested adults that reside in Somerset County are welcome to participate if space is still available.

3. Procedures

- a. Participants will be asked to participate in a health screening and preliminary fitness tests after the informed consent has been signed and returned. Participants will be asked to respond with a yes or no to the following questions as a preparticipation and/or health screening tool.
  1. Do you participate in regular exercise?
  2. Has a physician or other qualified health care provider ever diagnosed you with cardiac, peripheral vascular, cerebrovascular disease, or Type 1 or 2 diabetes?

3. Do you have any signs or symptoms suggestive of cardiovascular, renal, or metabolic disease including but not limited to: pain/discomfort in the chest, neck, jaw, or arms; shortness of breath at rest or with mild exertion; dizziness during exercise, ankle edema, palpitations (awareness of rapid beating of the heart) or tachycardia; or unusual fatigue or shortness of breath with usual activities?

The American College of Sports Medicine (ACSM) screening on a separate attachment will show how medical clearance is determined. Since the ACSM screening is limited in some regard, a Physical Activity Readiness Questionnaire Plus (PARQ+) will also be used as a precautionary measure prior to participation to gather additional information. The PARQ+ is located on a separate attachment. There is a line drawn through specific information related to a condition and/or medication because that information is not needed. The PARQ+ will be printed for the participants and the “please list” will be blacked out so that participants do not include this information. The information collected from the PARQ+ is only used to confirm whether or not the participant will need to obtain medical clearance prior to participation in any of the assessments and activities. The information is also used to determine proper exercise prescription for the intervention based on the participant’s current state of health. The participant will be asked to sign the PARQ+ and return it to the PI. The information collected from this will be stored in a sealed envelope that will be kept in a locked cabinet in the PI’s office. The PI is the only individual who has a key to the cabinet.

An ACSM screening algorithm and the PARQ+ will be used to determine if a participant needs medical clearance prior to participation in the preliminary fitness tests which is completed a week before the program begins. The preliminary fitness tests will include the curl up, the pushup, bench press, vertical jump, and the Rockport 1-mile or 1.5 mile walk test. The purpose of the fitness test is to acquire baseline data about physical fitness levels before implementation of the intervention. The preliminary fitness test will not be used to determine if an individual can or cannot participate. Participants will complete a Bio-electrical Impedance Analysis (BIA), body weight, and waist circumference measurements before and after the study. The BIA will be used to determine percent body fat, skeletal muscle, and body mass index. The PI will program the BIA device. The participant will be asked to step on a scale and hold the handle of the BIA device. The participant will be asked to hold the BIA device for up to 5 seconds until the device completes the scan. The weight of the BIA device is approximately 12 ounces. BIA devices are available for the public and may be purchased by the public. To measure the participant’s waist circumference, a tape measure will be placed around the participant’s waist on the outside of their shirt. The participant will be asked to identify where their belly button is and the participant will wrap the tape measure around their waist. One inch below the participant’s belly button is where the participant will be asked to place the tape measure. The BIA and waist circumference measurements will be conducted in the exercise science lab located in the Department of Kinesiology in Hytche Athletic Complex on UMES campus.

These data collected from participants will be recorded and stored on a password protected university-owned laptop. The participant’s middle name will be used as an

identifier until post assessments are complete. Post assessments are completed at the end of the program and will include all of the preliminary assessments.

Participants will progress from once to twice a week on non-consecutive days after 2 weeks of participating in the study. This will help participants adapt to the new movement and become familiar with an increase in physical activity. Participants have the option of whether to continue with the study for 12 weeks. Participants will report to Hytche Athletic Complex for a 60-minute combined aerobic and resistance group training session facilitated by the PI. The session will include pre-exercise stretching, an (aerobic) warm-up, weight training, (aerobic) recovery, and a period of post-exercise stretching. The warm-up and recovery will include 10 minutes of steady-state aerobic activity on the indoor or outdoor track. During these periods, walking, jogging, or cardio machines may be used at participant discretion. Static and/or dynamic stretching of each major muscle group will be taught and implemented. The resistance/weight training session will include 8-10 different exercises that target major muscle groups (legs, chest, and back). The time and intensity will progress from one set of 10-15 reps per exercise to three sets of 8-10 reps per exercise. The intensity follows the American College of Sports Medicine guidelines for exercise testing and prescription and will progress from low to moderate intensity (ACSM, 2021). Abdominal and low-back exercises will also be incorporated throughout the weight training portion to promote muscular balance. Participants can ask for an alternative method and/or not to participate in one or all of the exercises after they are demonstrated and explained.

- b. The BIA, bodyweight, waist circumference, pushup, curl-up, bench press, and the vertical jump test will take place in the exercise science lab of the Department of Kinesiology in Hytche Athletic Complex on the UMES campus. Males will complete pushups on their toes without their knees being down while women will complete pushups in the modified version with their knees down. An Airex cushion will be placed under both males and females as a precautionary measure if they are unable to complete a pushup. Participants will be given an exercise mat to complete their curl-up on the floor. For the bench press, the participant will lie on a bench that includes a barbell and free-weight plates, if applicable. The PI will spot all participants behind the bench with hands ready to catch the barbell. For the vertical jump test, participants will stand on a mat and jump straight up in the air to hit and/or move the rung. This will be performed on a mat to allow for a softer landing. The vertec is a piece of equipment used to measure leg power which is the result of leg strength. The vertec includes several mobile rungs. A standing reach height is measured first and then a jump height is measured. The reach height is measured by the participants extending their arms overhead in the air and walking past the vertec to move the rungs with their fingers. The jump height is measured by the rung that the participant hits/touches when he/she jumps straight up. The participant will jump three separate times with rest in between each. The participant is able to control when he/she wants to stop and therefore, the participant does not have to jump all three times. The PI will demonstrate all assessments and allow participants to ask questions throughout. The aerobic and resistance training activities that are a part of the intervention session will take place in the dance studio in Hytche Athletic Complex. The dance studio will have all equipment related to the session in the room. Some of the

aerobic and flexibility activities will take place in the main arena in Hytche Athletic Complex on the track.

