- c. The participants will be the direct beneficiaries of this study. Currently, there are limited to no opportunities for community residents to be physically active. Somerset County has the highest physical inactivity and physical health levels among surrounding counties. Expected benefits include improved weight maintenance, body composition, and health-related physical fitness. Participants can also expect to learn proper form and technique with flexibility, calisthenics, and resistance training exercises. Participants will also gain an understanding of how they can maintain physical activity levels despite the conclusion of the intervention. This study will contribute to existing research on health-focused community-health intervention programs in rural areas.
- d. Since the study is open to Somerset County community residents, the benefits will be distributed fairly. Participants will engage in the same program and receive the same services. It must be noted that participants may receive different levels of benefits based on individual motivation, consistency, and initial starting point in regards to physical activity. Children are not included in this study because children require a different training regime due to physical and neurological limitations associated with participation in a training session. Additionally, it is not appropriate for pregnant women to participate in this program. It would be difficult to assess changes in body composition and components of physical fitness as pregnant women undergo physiological changes that are relevant to being pregnant. For example, pregnant women may have a higher resting heart rate, lower aerobic capacity and/or exercise tolerance, and higher body fat levels. The purpose of this program contradicts some of the changes expected to take place with pregnant women and therefore the risks associated with their participation outweigh the potential benefits.

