- b. Interested participants may call, email, or access the google form through the link provided by the principal investigator on the invitation to participate. Once the participant expresses interest by providing their contact information, an individual appointment will be scheduled to explain the study and the procedures. The informed consent, ACSM screening algorithm, PARQ+, and supplemental informed consents, if applicable, will be explained to the participant. The participant will be given time to ask questions. If the participant is still interested in participating, he/she will be asked to sign the documents. At these individual meetings, each participant will be provided a copy of the informed consent for him/her to keep.
- c. The readability report for the informed consent was over 12th grade with an age of 19 to 20 years old.

7. Research Plan for Collection, Storage, and Analysis of Data

- a. Data will be collected using a tape measure and a bioelectrical impedance analysis (BIA) device. Participants will be asked to complete a fitness test which includes a bench press, vertical jump, pushup, curl up, and either a 1-mile walk or 1.5 run/walk test. Data collected is what the participant completes through counting or by using a stopwatch. Participants can choose not to complete some or all of the fitness test. The PI is responsible for supervising all sessions. The PI is certified through both national certifying organizations, the National Strength and Conditioning Association and the American College of Sports Medicine, for exercise program design, implementation, and safety. The PI is required to maintain three certifications through pre-approved continuing education through the certifying organization as well as maintaining a current Cardiopulmonary Resuscitation (CPR) and Automated External Defibrillator (AED) certification. Additionally, there is a licensed athletic trainer working in Hytche Athletic Complex.
- b. Data will be stored in an excel spreadsheet on a password-protected laptop loaned to the principal investigator from the university. The PI is the only individual who has access to the laptop.

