- c. Data will be analyzed for the mean and standard deviation of pre and post individual assessment data as a result of the intervention sessions. ANOVA with significance set at  $p<0.05$  will be used to determine the significance of the change in body weight, composition, waist circumference, and measures of fitness that may or may not have occurred. The mean and standard deviation of scores, pre and post, will be calculated and reported.
- d. The PI is the only individual who will have access to the data. Participants may request a copy of personal measurements/assessments prior to the conclusion of the study as pseudonyms may be replaced with numbers.
- e. The data will be kept for three years at the conclusion of the study.
- f. After the three-year period, the file will be deleted from the computer and the deleted folder will be emptied.

8. Conflict of Interest

- a. Potential conflict of interest includes receiving a grant from Somerset County Health Department (SCHD) for the development and implementation of a health intervention program for adults in Somerset County. This research effort and collection of data is not a condition of the funding received. This project may be carried out without intentions of a publication and/or presentation however, it has the potential to contribute to a body of knowledge on community health interventions and how they may be implemented. Additionally, results obtained from this project will be useful in applying for additional funding opportunities that will benefit the surrounding community. A narrative will be shared with SCHD at the completion of the project however, no raw data will be shared. The narrative will include results from the data analysis. The funding covers the equipment that will be needed, supplies for the participants, and salary. Equipment will include items such as the most accurate BIA home device, medicine/physio balls, exercise mats, stretching bands, and dumbbells. Supplies will include items such as hand towels, water, sanitizing wipes, and post-session snacks. Salary will be given to the PI for development and implementation of the intervention. This conflict will not affect the level of risk to the study participants and will be disclosed in the informed consent. Additionally, disclosure of this conflict of interest will be included in publications and/or presentations of the study results.

9. HIPPA Compliance

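### The primary outcome joins three domains with and/or and names no deciding measure, so improvement on any one of up to ten measures tested at p<0.05 could be reported as the primary result

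*Combined protocol and SAP*

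**What the plan says.** Section 1a states the aim "with a primary outcome of improving body weight, body composition and/or measures of fitness". It does not say which measure decides, how many must improve, or in which direction body weight should move. Section 4c adds "Expected benefits include improved weight maintenance, body composition, and health-related physical fitness", so holding weight steady might also count as a benefit.

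Section 3a shows what the domains contain. Body weight and waist are measured before and after. On body composition, "The BIA will be used to determine percent body fat, skeletal muscle, and body mass index". On fitness, "The preliminary fitness tests will include the curl up, the pushup, bench press, vertical jump", followed by a timed walk test offered in two versions.

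Section 7c sets significance at p<0.05 and says that ANOVA "will be used to determine the significance of the change in body weight, composition, waist circumference, and measures of fitness". Waist is tested there although section 1a does not name it. Section 7c also commits to descriptive results: "The mean and standard deviation of scores, pre and post, will be calculated and reported".

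On size, section 2d says "The project is limited to 15 individuals". There is one group. On completeness, section 7a says "Participants can choose not to complete some or all of the fitness test".

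**The concern.** A primary outcome is meant to fix, before the results are known, what would count as success. Here the conjunction leaves that open. Weight alone, any body-composition reading alone or any fitness test alone would fit the wording of section 1a, and section 7c puts each to the same 0.05 threshold. Each further measure is another chance for a random favourable change to be presented as the main finding.

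The results have a use beyond the participants. Section 5a says that the before and after results will be used to judge whether the intervention works. Section 8a says that a narrative including the analysis results goes to the county health department that funds the project, and that the results should help in seeking more funding. A plan that declares a primary outcome and a significance level for that purpose should say what would meet it.

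**Working it through.** The documents contain no sample-size, power or family-wise error figure, so there is nothing of the plan's own to reproduce beyond the 0.05 level.

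**Inputs from the documents**
- Significance level 0.05 (section 7c). A pre-post ANOVA with two time points does not distinguish direction, so a false *improvement* on one measure has probability 0.05/2 = 0.025.
- At most 15 participants, one group (section 2d).
- Measures listed in section 3a: body weight; waist; BIA percent fat, skeletal muscle and BMI; curl-up, push-up, bench press, vertical jump and walk test. That is 1 + 1 + 3 + 5 = 10.
- Bod Pod readings are left out. The February 2023 amendment plans them at weeks 8 and 12 only, so they have no baseline.

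**Counts used (*k*)**, expanded here from section 3a and not stated in the documents
- 3: one measure per domain in section 1a. This is a lower bound, since no composite or lead measure per domain is defined.
- 8: body weight, percent fat, skeletal muscle and five fitness tests. Waist is omitted because section 1a does not name it, and BMI because at fixed height it follows weight.
- 10: everything listed.

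**Assumptions**
- No true change on any measure.
- Each test is within person.
- Changes are equally correlated across measures, at 0, 0.5 or 0.9. The documents give no correlations.

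**Formula at correlation 0:** 1 − (1 − 0.025)^k
- k = 3: 1 − 0.975^3 = 0.073
- k = 8: 1 − 0.975^8 = 0.183
- k = 10: 1 − 0.975^10 = 0.224

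**With correlation:** simulation of within-person t tests at n = 15 (equivalent to repeated-measures ANOVA with two times), 200,000 runs per setting.

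| Measures | Correlation 0 | 0.5 | 0.9 |
|---|---|---|---|
| 1 | 2.5% | 2.5% | 2.5% |
| 3 | 7% | 6% | 4% |
| 8 | 18% | 13% | 6% |
| 10 | 22% | 15% | 7% |

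With 10 completers instead of 15, the eight-measure rates hardly move: 18%, 13% and 6%.

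**Direction of body weight.** If either a gain or a loss could count, that measure carries 0.05 instead of 0.025. Eight independent measures then give 1 − 0.975^7 × 0.95 = 0.204, or about 20%.

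**What one within-person primary test can detect** (two-sided 0.05, 80% power, in SDs of the within-person change): 0.78 SD with 15 participants and 1.00 SD with 10 completers.

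**The case against.** **The success rule is inferred.** Section 1a describes what the project offers and section 7c never says that one significant test shows the program works. That is correct. A reader might infer that the plan adopts a rule that any one significant measure suffices; the documents do not say so. What stands is narrower: nothing in them prevents the result from being reported that way.

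**The numbers rest on choices made here.** The count and the correlations are not in the documents. A reader might take 18% as the study's false-positive rate, but it is one corner of a range that runs from 4% to 22%. Even the lowest value exceeds the 2.5% for one test.

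**Section 7c does not name the ANOVA model.** A reader might infer that pre and post scores will be compared as if from separate groups, in which case this inflation would largely not appear. The documents point the other way: section 5a says each participant's identifier is used to assess before-after change, and section 3a keeps it until the post assessments are done. A within-person test is the natural reading, but it should be stated.

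**Small, uncontrolled program.** In one group of at most 15 people, formal multiplicity adjustment is partly a matter of preference. Section 8a says that the research is not a condition of the funding. The pre and post means and SDs promised in section 7c should place a lone significant result beside the other measures, so a reading that unfavourable results will be hidden is not supported. These points argue for a light remedy. They do not remove the need to say which measure is primary.

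**A larger threat remains.** Without a control group, familiarity with the tests or selective completion could produce a significant change even on one pre-named measure. That stands, and naming a primary does not cure it.

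**Conclusion.** The gap in the text is clear: sections 1a and 7c name no deciding measure, ranking or multiplicity rule, and no other section supplies one. As written, an improvement on any one measure can be reported as the primary result. Its size is illustrative, under the assumptions set out above: about 4-7% for three measures, 6-18% for eight and 7-22% for ten, against 2.5% for one test. Confidence is high in the gap and lower in any single figure. It should be fixed, because the remedy is a change of wording. It is not a finding that the plan intends selective reporting, nor that its analysis is unpaired.

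**What to change.** By dated amendment to sections 1a and 7c:

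1. Name one primary measure taken in all participants at baseline and week 12. The choice is the investigator's; BIA percent body fat is one example. An optional fitness test is a weaker choice because participants may skip it. If body weight is chosen, state which direction counts as improvement.
2. State that the primary is tested within person (paired or repeated-measures) at two-sided 0.05.
3. Report every other measure as secondary, with mean change and 95% CI, and state that a significant secondary result alone does not meet the primary outcome.
4. Report how many participants have both a baseline and a week-12 value for the primary measure, since they may leave at any time.

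**Timing.** The amendment should precede the collection or viewing of any post-assessment data. A cutoff at analysis would be too late, because the same investigator takes the measurements, enters them and sees individual results, including the week-8 Bod Pod readings. The amendment should say whether those readings had already been seen. The documents do not settle where the study stands: section 1a dates the program January 9 to March 31, 2022, while the amendment of February 2023 still looks ahead to weeks 8 and 12 in March and April. If post-assessment data have already been collected or seen, label all results exploratory.

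**Cost.** Wording changes and an IRB amendment, with no new data. There are fewer routes to a positive result, and the single primary test has 80% power only for changes of about 0.78 SD (1.00 SD with 10 completers). The lack of a control group still limits what a significant change can show, and the report should say so.

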- a. This research includes the collection of protected health information. The participant's anthropometrics (body weight and waist circumference) and body composition (BIA) will be recorded at the beginning and again at the conclusion of the 12 weeks. The PI, however, will not be contacting health care providers for any reason. Participants are allowed to receive a copy of personal measurements and/or assessments to give to their physician if it is requested prior to the conclusion of the study. Pseudonyms will be replaced with numbers therefore it will be impossible to determine a specific individual's results at the conclusion of the study. The health screening will be an interview with the potential subject. The interview includes three questions to determine if medical clearance is needed prior to participation as a precautionary measure. The answers to

these questions will not be shared with anyone. The questions for the ACSM preparticipation screening include:

1. Do you participate in regular exercise?
2. Has a physician or other qualified health care provider ever diagnosed you with cardiac, peripheral vascular, cerebrovascular disease, or Type 1 or 2 diabetes?
3. Do you have any signs or symptoms suggestive of cardiovascular, renal, or metabolic disease including but not limited to: pain/discomfort in the chest, neck, jaw, or arms; shortness of breath at rest or with mild exertion; dizziness during exercise, ankle edema, palpitations (awareness of rapid beating of the heart) or tachycardia; or unusual fatigue or shortness of breath with usual activities?

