The ACSM screening on a separate attachment will show how medical clearance is determined. Since the ACSM screening is limited in some regard, a Physical Activity Readiness Questionnaire Plus (PARQ+) will also be used as a precautionary measure prior to participation to gather additional information. The PARQ+ is located on a separate attachment. There is a line drawn through specific information related to a condition and/or medication because that information is not needed. The PARQ+ will be printed for the participants and the “please list” will be blacked out so that participants do not include this information. The information collected from the PARQ+ is only used to confirm whether or not the participant will need to obtain medical clearance prior to participation in any of the assessments and activities. The information is also used to determine proper exercise prescription for the intervention based on the participant’s current state of health. The participant will be asked to sign the document. The information collected from this will be stored in a sealed envelope that will be kept in a locked cabinet in the PI’s office. The PI is the only individual who has a key to the cabinet.

- b. The responses from the interview will be used to determine if medical clearance is necessary to participate in the study as a precautionary measure.

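### The screening question on diagnosed disease leaves out renal disease, which the adjacent symptom question names, and the supplied text does not show whether the PARQ+ closes that gap.

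*Combined protocol and SAP*

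**What the plan says.** Section 3a (Procedures) lists three yes/no questions, and section 9a (HIPPA Compliance) prints them again. Question 1 asks about regular exercise. Question 2 concerns diagnoses: "Has a physician or other qualified health care provider ever diagnosed you with cardiac, peripheral vascular, cerebrovascular disease, or Type 1 or 2 diabetes". Question 3 concerns current complaints: "Do you have any signs or symptoms suggestive of cardiovascular, renal, or metabolic disease", followed by an open list of examples such as chest pain, ankle edema and unusual fatigue.

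The plan describes the route to medical clearance in several places:

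- Section 9a, on the interview: "The interview includes three questions to determine if medical clearance is needed prior to participation as a precautionary measure".
- Section 9b: "The responses from the interview will be used to determine if medical clearance is necessary to participate in the study".
- Section 3a, on what is applied before the preliminary fitness tests: "An ACSM screening algorithm and the PARQ+ will be used to determine if a participant needs medical clearance".
- Sections 3a and 9a, on why a second form was added: "Since the ACSM screening is limited in some regard, a Physical Activity Readiness Questionnaire Plus (PARQ+) will also be used".
- Sections 3a and 9a, on the decision rule itself: the ACSM "screening on a separate attachment will show how medical clearance is determined".

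The PARQ+ is also an attachment, and it has been altered: "There is a line drawn through specific information related to a condition and/or medication because that information is not needed".

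**The concern.** The two questions sit side by side and feed the same decision, yet they do not cover the same diseases. By naming renal disease in question 3, the plan treats it as relevant to screening. Question 2 gives a person no place to report it as a diagnosis. Someone whose kidney disease is known but currently silent could answer both questions truthfully and leave no trace of it in the interview.

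Screening is the main safeguard before exercise in this study. Enrolment is first come, first served, with no upper age limit and no selection on characteristics (sections 2a and 2d). Section 3a says the fitness tests are not used to decide who may take part. Section 4a notes that resistance training may raise heart rate and blood pressure. It therefore matters whether the screen asks what it is meant to ask.

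**Working it through.** The plan gives no figure to reproduce, and no arithmetic bears on the point. The check is a comparison of texts.

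**Step 1: compare the disease lists.**

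| Disease class | Question 2 (diagnosed) | Question 3 (signs or symptoms) |
|---|---|---|
| Cardiovascular | cardiac, peripheral vascular, cerebrovascular | named |
| Metabolic | Type 1 or 2 diabetes only | named as a class |
| Renal | not named | named |

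The clear gap is renal. The metabolic class is also narrower in question 2, because diabetes is the only condition listed there.

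**Step 2: rule out a copying slip.** Sections 3a and 9a print both questions with the same disease lists. The omission is in both copies, so it is neither an error in one printing nor damage from reading the PDF.

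**Step 3: look for open wording that might rescue question 2.** Question 2 is a closed list. The open-ended phrase in question 3 extends its examples of signs and symptoms. It does not extend the diagnoses in question 2.

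**Step 4: trace one person through the interview.** Take a person with diagnosed renal disease, no diagnosis listed in question 2, and no signs or symptoms.

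- Question 1 is about exercise habit and carries no information on disease.
- Question 2: the truthful answer is no.
- Question 3: the truthful answer is no.

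The interview then records neither known disease nor symptoms. All three conditions are needed. A person with renal disease who also has diabetes or a listed vascular diagnosis answers yes to question 2. One with ankle edema or unusual fatigue answers yes to question 3.

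**Step 5: trace the same person through the rest of the clearance process.** Under section 3a the PARQ+ also bears on clearance. Whether this person is flagged depends on whether a PARQ+ item covers kidney disease and on how the attached ACSM algorithm treats the answers. Neither attachment is in the supplied text. The struck-out condition and medication details mean that the form would not record a named condition, but a yes/no item could still flag the person. The outcome cannot be determined from the documents.

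**Step 6: compare the statements of what decides clearance.** Section 3a names the ACSM algorithm and the PARQ+. Section 9a describes the interview as serving this purpose and also gives the PARQ+ a confirming role. Section 9b mentions only the interview, though it does not say that nothing else counts. The text does not say what follows when the interview is negative and the PARQ+ is positive.

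**The case against.** The strongest reply is that the interview was never meant to stand alone. Section 3a gives the PARQ+ a part in the clearance decision, and the plan says openly that it was added because the ACSM questions are limited. Section 9b follows directly on text in 9a that gives the PARQ+ the same role, so 9b need not be read as excluding it. No passage requires a diagnosis question and a symptom question to share one list. There are other safeguards as well: body weight only in weeks one and two, ratings of perceived exertion throughout each session with termination by the investigator (section 4b), and supervision of all sessions with freedom to skip fitness tests (section 7a).

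Most of this stands, and it limits what may be concluded. A reader might infer that a person with silent kidney disease would go on to the bench press, the other tests and 12 weeks of training without clearance. The documents do not support that, because the second layer exists and its content cannot be seen. They do not support the opposite inference either, that the PARQ+ certainly closes the gap.

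A reader might also want a probability that at least one such person enrols. The documents give no prevalence, and 15 is a cap rather than an expected enrolment. Under 1 − (1 − p)^15, an assumed p of 1% gives 14% and an assumed p of 2% gives 26%, so the result only reflects the assumption. The relevant p would also have to leave out people caught by question 2, question 3 or the PARQ+.

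What the objection does not remove is the mismatch between the two questions, or the difference between 9b and 3a over which instruments decide.

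**Conclusion.** The point holds as a minor inconsistency with a bearing on participant safety. Questions 2 and 3 use different disease lists in both printings. The interview alone misses a person with diagnosed, symptom-free renal disease and no question 2 diagnosis, although sections 9a and 9b use that interview in deciding on clearance. Whether the whole process misses such a person is unknown, because it turns on two attachments that were not supplied.

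No size can be put on it from the documents. The outcomes, the pre/post comparison and the planned ANOVA are not affected. The conclusion rests only on the printed wording and on participants answering truthfully. Which list or clearance rule is clinically right is not judged here.

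**What to change.** Reconcile the disease lists of questions 2 and 3, and make the same change in sections 3a and 9a. Check the reconciled questions against the attached ACSM algorithm and the altered PARQ+, so that all three agree on which diseases are asked about. Bring section 9b into line with section 3a, which says that the algorithm and the PARQ+ are both used to determine clearance. The choice of list and of clearance rule belongs to the investigator and the IRB.

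The cost is a few words in two printed questions and one sentence in 9b. The downside is that an occasional extra participant may need a clearance note. The Bod Pod amendment of February 2023 refers to the pre-assessment in the past tense, so baseline screening of this cohort appears to be over. The wording change would then mainly serve any later cohort.
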